#### 6.2.1.4 PrEP Comparison Component Maternal Labor and Delivery Visit

*Note: The calendar will reset after delivery for postpartum visits, with the delivery date considered as Day 0, and subsequent visits calculated from this date.*

The maternal labor and delivery visit will be conducted within 14 days of delivery. If the delivery visit is conducted within 30 days of the last visit, procedures do not need to be repeated except for the rapid HIV test, HIV RNA test and plasma storage for future resistance testing. If the mother does not deliver a live born infant the mother should still complete the Delivery Visit and all subsequent postpartum visits if she is willing to do so.

PrEP Comparison Component Maternal Labor and Delivery Visit Procedures (L/D +14 days)	
Administrative and Regulatory	

Review locator information

Behavioral and Counseling	

Qualitative Interview IDI Visit: to take place at the L/D visit or at an alternative date [see Section 6.2.1.8]

 
Cohort 1 and Cohort 2/Step 2 only:
 

iNSC with drug level feedback [see Section 5.3.2]

 
Cohort 2 only:
 

iNSC [see Section 5.3.2]

Assess for social harms [see Section 13.6]

Clinical	

Obtain interim medical/medications history, including pregnancy outcome

Perform targeted physical exam

Identify/review/update adverse events

Perform additional evaluations per Section 8 and/or if clinically indicated (consult CMC if indicated)

Laboratory	Blood 
Collect blood for:
 

HIV RNA test

Store plasma for HIV drug resistance testing

Rapid HIV test [see Section 6.3 in the event the test is (+)]

TFV- DP level (DBS)

ALT, Creatinine, and CrCl

Other	Radiology 
DXA scan of:
 

Hip

Lumbar Spine

Study Product	
Cohort 1 and Cohort 2/Step 2 only:	

Prescribe and dispense study drug

	

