### **6.2.2.1 PrEP Comparison Component Infant Birth Visit**

The allowable window for all evaluations expected at birth is within 14 days after birth; however, it is understood that sites may not be able to conduct the DXA scan on the same date as the other evaluations and may not be able to arrange a scan within that window. Sites should make every effort to schedule the DXA scan to take place within the 14-day window, but up to 21 days is allowed. See [Section 6.14](#) for further details.

PrEP Comparison Component Infant Birth Visit Procedures (Birth +14 days)		
Clinical		

• Obtain birth history, interim medical and medications history since birth, and feeding history since birth

• Perform complete infant physical exam

Laboratory	Blood	Collect blood for: 

• Creatinine

• TFV-DP level (DBS) (for storage)

	Other	

• Rectal swabs or fresh stool for microbiome

Other		DXA scan of: 

• Whole body

• Lumbar Spine

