#### **6.14 Infant DXA Scans**

Infants in the PrEP Comparison Component will undergo DXA scans of the whole body and lumbar spine at their Birth Visit and of the lumbar spine Week 26 postpartum. Scans will be performed according to standardized procedures described in the study-specific MOP. Scan images will be transferred electronically for centralized reading and results will be transmitted electronically from the central readers to the Data Management Center (DMC). The centralized readings of all scans will be made available to the study sites after the last scan has been read centrally. However, if an infant experiences a bone fracture subsequent to his or her scan, the result of his or her scan will be provided to the site as soon as available.

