*Analyses of infant safety outcomes re: bone health and creatinine clearance:* To address Primary Objective 2.3.2, to evaluate infant safety outcomes, (CrCl measured by Schwartz equation at birth and 26 weeks anthropometric growth measures at birth and 26 weeks, bone mineral content measured by dual energy X-ray absorptiometry (DXA) at birth and 26 weeks), mean length-for-age z-scores for the growth parameters and mean grams for BMC will be calculated, and means will be compared between infants in Cohort 1 and infants in Cohort 2 using two sample t-tests at each time point of evaluation. If normality assumptions are not met the Wilcoxon Rank Sum test will be used to evaluate differences in these endpoints by Cohort.

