### **Visit Scheduling and Procedural Considerations**

- The allowable visit windows for all maternal and infant follow-up visits are extended by  $\pm 7$  days, as follows:
  - Maternal antepartum visits at Weeks 4, 8, and 12: allowable visit window is expanded to  $\pm 14$  days.
  - Maternal antepartum visits at Weeks 24 and 36: allowable window is expanded to  $\pm 21$  days.
  - Maternal Labor and Delivery Visit and Infant Birth Visit: allowable window is expanded to up to 21 days after delivery/birth.
  - Maternal and Infant PP Weeks 6, 14, and 26: allowable visit window is expanded to  $\pm 21$  days.
- DXA scans are required at the Maternal Labor and Delivery Visit, Infant Birth Visit, and Maternal and Infant Week 26 visits. It is understood that sites may not be able to conduct the maternal and/or infant DXA scans on the same date as the other evaluations for these visits, and may not be able to arrange a scan within the corresponding visit windows. Sites should make every effort to schedule the DXA scan to take place within these windows, but up to 28 days is allowed.
- Sites may make use of these expanded allowable visit windows as needed, however, the visit windows specified in protocol [Section 6](#) remain the target and sites are encouraged to continue scheduling within these target windows whenever possible. Sites should consider current or anticipated operational disruptions or closures when scheduling visits and should schedule visits early or late in the allowable window, as appropriate. Visits conducted outside of allowable windows are also preferred to missed visits
- If it is not possible to conduct study visits in-person at the study site, visit procedures may be performed off-site or remotely (e.g., by telephone) as described below. Site investigators must ensure that standard operating procedures (SOPs) are in place for off-site and remote procedures.

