3.2 Primary Outcome Measure(s) for PrEP Comparison Component

PrEP adherence:

- TFV-DP drug concentration level in Dried Blood Spots (DBS)

Maternal Adverse Events:

- Maternal Grade 3 or higher adverse events (signs, symptoms, labs, and diagnoses)
- Maternal Grade 2 or higher chemistry abnormalities

Adverse Pregnancy Outcomes:

Composite outcome of

- Spontaneous abortion (occurring at <20 weeks gestation)
- Stillbirth (occurring at ≥ 20 weeks gestation)
- Preterm delivery (<37 completed weeks' gestation)
- Small for gestational age (<10th percentile using **INTERGROWTH-21st** norms and ultrasound derived gestational age at delivery)

Infant Safety:

Infant Adverse Events

- Infant death within the first 26 weeks of life
- Infant Grade 3 or higher adverse events (signs, symptoms, labs, diagnoses) reported between birth and 26 weeks postpartum

Infant Growth and Development

- Infant bone mineral content based on DXA scan of the whole body (WB-BMC) at birth and lumbar spine (LS-BMC) at birth and 26 weeks postpartum
- Infant creatinine and CrCl rate at birth and 26 weeks postpartum measured by Schwartz equation
- Infant length for age z-score at birth and 26 weeks postpartum

4 Definitions

Baseline

Maternal baseline is defined as the measurement on or closest to the study entry date, and infant baseline is defined as the measurement at birth. For the PrEP Comparison Component analyses characterizing the proportion with optimal adherence to PrEP among women in Cohort 2 who subsequently decide to initiate PrEP, baseline is defined as the date initiating PrEP.

Visit Windows for Analysis

All analyses summarizing or referring to data by visit week include a visit window around the applicable study visit week. For maternal antepartum study visit weeks 4, 8, and 12 the visit window is +/- 14 days. The visit window is +/- 21 days for antepartum visit weeks 24 and 36. The Labor and Delivery/Infant birth visit may occur as soon as possible after delivery through 21 days postpartum. The visit window is +/- 21 days for the maternal and infant 6- week postpartum, 14-week postpartum, and 26-week postpartum visits.

Analysis Sets

PK Component:

- **PK Adherence Set:** All maternal participants on PrEP, including those in Group 1 and those in Group 2

PrEP Comparison Component:

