Difference in mean infant growth and development outcomes between PrEP exposed (in Cohort 1 and Cohort 2 step 2) and PrEP unexposed infants (infants in Cohort 2) at birth and 26 weeks of age	Means will be estimated and compared between PrEP-exposed and PrEP unexposed infants using two sample t-tests at each time point of evaluation, or Wilcoxon rank sum tests as appropriate to evaluate differences in these endpoints between PrEP-exposed and PrEP unexposed infants.

7. Report Contents

An overview of the contents of the final analysis report for the PrEP Comparison Component is outlined below. Additional details of the final analysis report contents are provided in the AIP.

- CONSORT diagram
- Study entry:
 - Screening
 - Accrual
 - Eligibility
- Baseline characteristics (reported in ClinicalTrials.gov)
 - Maternal characteristics at baseline
 - Infant characteristics at birth
- Study retention (reported in ClinicalTrials.gov)
 - By Cohort and study visit
- Treatment status:
 - By Cohort (Cohort 1-PrEP, Cohort 2-No PrEP)
 - Frequency and Timing of switching from No PreP to PrEP (i.e., Cohort 2 step change)
- PrEP discontinuation, and PrEP restart (if applicable)
 - PrEP discontinuation reasons
- PrEP adherence:
 - N (%) with optimal adherence at each visit, overall, during pregnancy, and postpartum, and by gestational age group at enrollment
 - Number and timing of visits missed when assessment of PrEP adherence was expected
- Maternal safety outcomes
 - By PrEP exposure
 - During pregnancy and postpartum
- Pregnancy Outcomes
 - Overall and by PrEP exposure
- Infant safety outcomes
 - Overall, by PrEP exposure

8 Associated Documents

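### The main comparison of infant bone mineral content, creatinine and CrCl ignores age at measurement and site, although birth values may come from day 0 to day 21 (DXA to day 28) and Week 26 values from ±21 days

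*SAP*

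**What the plan says.** SAP 6.3.5 sets the analysis of the fifth primary estimand: "Means will be estimated and compared between PrEP-exposed and PrEP unexposed infants using two sample t-tests at each time point of evaluation". The Wilcoxon test is named there as the fallback. The outcomes are whole-body BMC at birth, lumbar spine BMC at birth and 26 weeks, creatinine and Schwartz CrCl at both times, and length-for-age z-score at both times. Protocol 9.2.6 describes the same unadjusted comparison: "mean length-for-age z-scores for the growth parameters and mean grams for BMC will be calculated". Of these outcomes only length is standardised for age. Protocol 8.1.4 notes that no normal ranges for infant BMC are in current use.

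The measurement windows are wide:

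- SAP section 4, birth: "The Labor and Delivery/Infant birth visit may occur as soon as possible after delivery through 21 days postpartum".
- SAP section 4, later visits: "The visit window is +/- 21 days for the maternal and infant 6- week postpartum, 14-week postpartum, and 26-week postpartum visits".
- Protocol 6.2.2.1 sets birth evaluations at 14 days, with an exception for DXA: "Sites should make every effort to schedule the DXA scan to take place within the 14-day window, but up to 21 days is allowed".
- Protocol Appendix X (COVID-19 disruption) extends the birth visit to 21 days, and for DXA says: "Sites should make every effort to schedule the DXA scan to take place within these windows, but up to 28 days is allowed".

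Protocol 9.2.1 promises that potential confounders will be measured and adjusted for in multivariable models. SAP 6.3.1 to 6.3.4 are each followed by supplemental analyses that include such models. SAP 6.3.5 has none.

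**The concern.** An infant outcome that changes with age, recorded anywhere in a window of three or four weeks, carries variation that has nothing to do with PrEP. A two-sample test leaves that variation in the error term. If exposed and unexposed infants are measured at different average ages, or are spread differently over sites, part of the difference in means reflects timing or site. Women choose their cohort, so randomisation does not protect against such differences. At stake are some precision for a contrast that protocol Table 11 sizes at about 81% power, and the readability of a primary infant safety result. If a difference appeared and measurement age proved unequal, any adjustment would then have to be chosen after seeing the data.

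**Working it through.** **Inputs from the documents.** Protocol 9.2.4 and Table 11: 200 and 100 infants; whole-body BMC at birth with mean 63.8 g and SD 16.6 g; difference 0.35 × 16.6 = 5.81 g; stated power 81%. Alpha 0.05 is stated for Table 10 and assumed two-sided here. The windows are those listed above.

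**Assumptions.** The documents give no slope of BMC on age, so 0.25, 0.5 and 1.0 g/day are used as a range. The top value is high: 21 days × 1.0 = 21 g, a third of the 63.8 g mean. Scan age is taken as uniform over the window.

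**Step 1: reproduce the plan's figure.** SE = 16.6 × √(1/200 + 1/100) = 2.033 g. 5.81 / 2.033 = 2.858. Power = Φ(2.858 − 1.960) = 81.5%; the noncentral t gives 81.3%. Table 11 reproduces, and 81.3% is the reference below.

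**Step 2: timing spread equal in both groups.** Over 21 days the SD of age is 21/√12 = 6.06 days. There are two cases: the 16.6 g SD excludes this spread (total SD = √(16.6² + (slope × 6.06)²)), or it already includes it and adjustment removes it (residual SD = √(16.6² − (slope × 6.06)²)).

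| Slope (g/day) | SD due to age (g) | Total SD if excluded (g) | Power, unadjusted | Residual SD if included (g) | Power, adjusted |
|---|---|---|---|---|---|
| 0.25 | 1.52 | 16.67 | 81.0% | 16.53 | 81.6% |
| 0.5 | 3.03 | 16.87 | 80.0% | 16.32 | 82.6% |
| 1.0 | 6.06 | 17.67 | 76.3% | 15.45 | 86.4% |

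Against 81.3%, the loss is 0.3, 1.3 or 5.0 points in the first case, and the gain from adjusting is 0.3, 1.3 or 5.1 points in the second. If scans were spread evenly to day 28, which Appendix X permits but does not target, the SD of age is 28/√12 = 8.08 days and unadjusted power in the first case is 80.7%, 79.0% or 72.6%. In none of these cases is the difference in means biased.

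**Step 3: mean age differs by exposure.** Bias = gap in days × slope. For 3 days at 0.5 g/day, bias = 1.5 g and 1.5 / 2.033 = 0.738. Type I error = 1 − Φ(1.960 − 0.738) + Φ(−1.960 − 0.738) = 11.4%. If the bias masks a true 5.81 g deficit, power = Φ((5.81 − 1.5)/2.033 − 1.960) = 56%.

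| Gap (days) | Slope (g/day) | Bias (g) | Type I error |
|---|---|---|---|
| 1 | 0.5 | 0.5 | 5.7% |
| 3 | 0.25 | 0.75 | 6.6% |
| 3 | 0.5 | 1.5 | 11.4% |
| 3 | 1.0 | 3.0 | 31.4% |

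The gaps are illustrations; nothing in the documents points to any particular value.

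**Not sized.** For creatinine, CrCl and lumbar spine BMC the documents give neither an SD nor an age trend, so no figure is offered.

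**The case against.** The strongest reply is that nothing shows the groups will differ in measurement age. Both cohorts share the same infant schedule, windows and DXA requirements, and without a gap the t-test is unbiased. That stands, and it limits the point to modest precision plus a risk that cannot be ruled out. The 16.6 g SD may already contain the timing spread, and Table 11 reproduces, so no sizing error is claimed. The 21-day limit for creatinine comes from the SAP and Appendix X; the protocol's standard limit is 14 days, and Appendix X keeps the standard windows as the target. Site balance is also watched: protocol 9.2.5 has the CMC monitor it and act on divergence. Monitoring reduces imbalance but does not adjust for what remains.

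Two stronger readings are tempting. A reader might infer that PrEP users attend the delivery visit earlier, because protocol 6.2.1.4 dispenses study drug only to them, and that the contrast is therefore biased. That is conjecture; no text reports or predicts different attendance. A reader might also infer that scanners differ between sites and add machine error. The documents give no number, make or calibration of scanners, and protocol 6.14 says "Scans will be performed according to standardized procedures described in the study-specific MOP" and provides for central reading. Cross-calibration may be covered in that manual.

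It could also be said that the Analysis Implementation Plan will supply the model. SAP 1.1 gives that document table outlines, figures and coding descriptions, and keeps the analytic approach for every primary estimand in the SAP. The main model therefore belongs in 6.3.5.

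**Conclusion.** The point holds as an inexpensive improvement to a primary infant safety analysis. SAP 6.3.5 leaves age at measurement and site out of the comparison of BMC, creatinine and CrCl, and does not carry through the adjustment promised in protocol 9.2.1. With equal timing in both groups, the cost for whole-body BMC is about 0 to 5 power points over a 21-day window, given uniform scan age and slopes up to 1 g/day. Bias requires measurement age or site mix to differ by exposure; that is possible with self-selected cohorts at several sites, but it is not shown. The 1.5 g and 11% figures describe one assumed case and do not predict what will happen. The documents do not support saying that the contrast is biased, that scanner differences are present, or that Table 11 is wrong. One gap is definite: Appendix X allows a birth DXA up to day 28, the SAP birth window ends at day 21, and the SAP does not say what happens to scans in between.

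**What to change.** In SAP 6.3.5:

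- Make the main analysis of BMC, creatinine and CrCl, at each time point, a linear regression on exposure, age in days at measurement, infant sex and site. The exposure coefficient is still a difference in means, so the stated summary measure is kept.
- Retain the t-test or Wilcoxon test as unadjusted support.
- Report the distribution of measurement age by exposure group at birth and at Week 26.
- State how DXA scans on days 22 to 28 are handled. The 28-day allowance in Appendix X also covers Week 26 scans, so say the same for those beyond ±21 days.
- Treat log-transformed creatinine, and models with infant length or gestational age, as sensitivity or secondary analyses only. The first changes the summary measure; the others may condition on the causal path.
- Leave the length-for-age z-score analysis as it is.

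The cost is SAP wording and slightly more analysis work, since visit dates, sex and site are already collected. The small downside is that the model assumes a roughly linear age trend within each window.

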Attachment 1: Timetable for Primary Analysis and Manuscript

Event	Responsible party	Weeks from primary completion date (PCD)
Primary completion date (PCD)		PCD
Clinical data entry termination	Sites	PCD + 4 weeks
Initial database clean-up complete, including 
- DAERS reconciliation complete- TSDV complete	PDM and LDM	PCD + 12 weeks
Clinical database closure/freeze complete/eCRF sign-off by site investigators	PDM and Sites	PCD + 15 weeks
SDTM ARMCD populated	SDTM Specialist	PCD + 16 weeks
Complete SDTM on production server	SDTM Specialist	PCD + 16 weeks
Clinical database lock and primary laboratory database lock	Chief Data Manager and LDM Leadership	PCD + 17 weeks
Final SDTM on production server	SDTM Specialist	PCD + 18 weeks
Primary analysis report to Protocol Chairs/Writing Team	Protocol statisticians	PCD + 22 weeks

9 Appendix: Adherence Interpretations

The following Appendix Tables are adherence interpretations and categories based on TFV-DP Concentration (fmol/punch) in Dried Blood Spots (DBS) from the PK Component.

Appendix Table 1: Pregnant Women TFV-DP Concentrations in DBS at <=6 Weeks on PrEP and >6 Weeks and Beyond

Interpretation	≤ 6 Weeks on PrEP	> 6 Weeks on PrEP and Beyond
Green Zone Consistent with Highest levels of protection	≥600	≥650
Yellow Zone Consistent with some but incomplete levels of protection	150-599	200-649
Red Zone Consistent with low to no levels of protection	<150	<200

Appendix Table 2: Postpartum Women TFV-DP concentrations in DBS at <=6 Weeks on PrEP and >6 Weeks and Beyond

Interpretation	≤ 6 Weeks on PrEP	> 6 Weeks on PrEP and Beyond
Green Zone Consistent with Highest levels of protection	≥700	≥1050
Yellow Zone Consistent with some but incomplete levels of protection	200-699	300-1049
Red Zone Consistent with low to no levels of protection	<200	<300
